#### Handling Missing Data

Since each assessment involves a relatively brief self-administered instrument, the amount of missing data due to failure to provide data was minimal. The largest source of missing data was participant dropout. Of the 1360 participants in the study cohort 778 (57.2%) responded to the 48-hour survey, 681 (50.1%) responded to the 3-month survey, 676 (49.7%) responded to the 6-month survey, and 575 (42.3%) responded to both the 3-month survey and the 6-month survey.

Consequently, to minimize bias due to attrition, we employed multiple imputation so that every regression model could be fit to all available data while invoking the mild assumption that the data were missing at random. Imputation was performed on the data in wide format (one record per case) to correctly account for dependence in multiple observations per case. In models testing a time by treatment group, missing data were imputed separately for intervention cases and control cases. Imputation models contained all variables in the analysis model (including the outcome), baseline variables identified as correlates of retention, and indicator variables representing recruitment site (SBHC).

#### Heterogeneity of Treatment Effects

A concern in any cluster randomized control trial is whether or not the treatment effect is robust across sites. However, small per site sample sizes preclude direct comparisons between sites because of a lack of statistical power. We investigated the sensitivity of the intervention effect to recruitment site (SBHC) in the two primary outcomes where we assessed changes from baseline to

3-month and 6-month follow-up: contraception use self-efficacy (Aim 1c, Primary Outcome 2) and non-barrier contraception use (Aim 3b, Primary Outcome 3). For both outcomes, the time by treatment group interaction served as the direct test of the intervention effect. With three time points and two treatment groups, the interaction was represented by two parameter estimates. The sensitivity analysis employed a jack-knife technique where the analysis is repeated but with participants from one intervention SBHC removed from the analysis. Since there were 9 SBHCs randomly assigned to each treatment group, the jack-knife technique required 9 new models be assessed.

Table 2 reports the point estimate, 95% confidence interval, and p-value for each parameter obtained from the mixed effects regression analysis model including all 9 intervention SBHCs plus the range of parameter estimates and p-values obtained from the jack-knife analyses (models that included only 8 intervention SBHCs).

**Table 2. Parameter Estimates from Sensitivity Analyses Compared to Parameter Estimates from Analytic Models for Two Primary Outcomes**

Outcome	Interaction Parameter	Estimate	Analytic Model		Sensitivity Analyses	
			95% CI	p-value	Estimates	p-value
Contraception Use Self-efficacy	1	0.816	-0.482, 2.115	.218	0.477-1.086	.098-.408
	2	1.576	0.377, 2.774	.010	1.269-1.729	.006-.037
Non-barrier Contraception	1	1.190	0.043, 2.338	.042	1.128-1.350	.024-.063
	2	1.711	0.529, 2.544	.005	1.511-1.936	.003-.012

For both outcomes, the data suggest the intervention effect is not sensitive to recruitment site (SBHC).

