### Analytical and statistical approaches

We assessed the effect of the intervention by looking for differences over time between the control (usual care) group and intervention (Health-E You app) group in contraception use self-efficacy and self-reported use of non-barrier contraception at follow-up. Specifically we hypothesized, assuming group equivalence at baseline, that 3 months and 6 months post-baseline the intervention group, compared to the control group, would have higher mean contraception use self-efficacy (Aim 1c, Primary Outcome 2) and a higher proportion would be using effective (i.e., non-barrier) contraception (pill, patch, ring, shot, IUD, or implant) (Aim3b, Primary Outcome 3).

We assessed the effect of the intervention using generalized mixed effects models estimated by maximum likelihood (mixed effects linear regression to assess self-efficacy, mixed effects logistic regression to assess non-barrier contraception use). These models included the repeated outcome measure as the response variable as well as terms for the intercept, an indicator of treatment of group (intervention vs. control), a time effect (baseline, 3-month follow-up, 6-month follow-up), the time by treatment group interaction, and three covariates that clinical experience and thre research literature suggest could influence the outcome: age (rage was 14-18), whether the purpose of the clinic visit was related to pregnancy or contraception (a time invariant covariate), and whether the participant engaged in sexual intercourse in the past 3 months (a time varying covariate). We fit models with random intercepts and slopes over time to accommodate the repeated measures gathered from each subject and to allow subject-specific changes in the responses over time. The time treatment group interaction was the direct test if the intervention effect. Computation of p-values was based on robust variance estimation that adjusted for a potential lack of independence between observations due to clustering by recruitment site (SBHC).

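### The leave-one-clinic-out check drops only the 9 intervention clinics, but its conclusion covers recruitment site without limit; the influence of the 9 control clinics was not examined

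*Combined protocol and SAP*

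**What the plan says.** All of the following is in the combined protocol and SAP, mainly under Heterogeneity of Treatment Effects.

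- **Purpose.** The section asks whether the effect holds across sites. It examines sensitivity to recruitment site for two primary outcomes, contraception use self-efficacy and non-barrier contraception use. This aim is not restricted to one arm.
- **Effect under test.** "For both outcomes, the time by treatment group interaction served as the direct test of the intervention effect". Each outcome has two interaction parameters.
- **Method.** "the analysis is repeated but with participants from one intervention SBHC removed from the analysis". The count of models is explained as follows: "Since there were 9 SBHCs randomly assigned to each treatment group, the jack-knife technique required 9 new models be assessed". Table 2 is introduced as giving "the range of parameter estimates and p-values obtained from the jack-knife analyses (models that included only 8 intervention SBHCs").
- **Conclusion.** "For both outcomes, the data suggest the intervention effect is not sensitive to recruitment site (SBHC").

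The clinics also enter the analysis in two other places. Under Analytical and statistical approaches, p-values rest on "robust variance estimation that adjusted for a potential lack of independence between observations due to clustering by recruitment site". Under Handling Missing Data, the imputation models include "indicator variables representing recruitment site (SBHC").

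**The concern.** The interaction compares the change over time in the intervention arm with the change over time in the control arm. An unusual control clinic can shift the second part of that comparison just as an unusual intervention clinic can shift the first. Clinics in both arms are recruitment sites, and clinics were the randomized units. A check that drops clinics from one arm only therefore answers a narrower question, namely whether a single clinic using the app drives the result. The closing sentence answers the wider question.

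At stake is a statement of robustness for two primary outcomes in a trial with 18 clusters. A reader who relies on that sentence will believe that the influence of every clinic was checked, when half of them were not.

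**Working it through.** **1. Count of models.** Inputs: 9 clinics per arm, 18 in total (Study Overview; Heterogeneity of Treatment Effects). Dropping each intervention clinic once gives 9 models, which reproduces the stated figure. Dropping each randomized clinic once gives 9 + 9 = 18. The reported check covers 9/18 = 50% of clinics.

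**2. Is control-clinic influence covered elsewhere?** Robust variance adjusts p-values for dependence within clinics. Site indicators in the imputation models affect how missing values are filled in. Neither shows how far the estimate moves when one clinic is left out. No section describes omitting a control clinic or gives a reason for not doing so.

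**3. What the intervention-clinic deletions show (Table 2).** The full-model SE is the CI width divided by 3.92:

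- Self-efficacy 1: (2.115 + 0.482)/3.92 = 0.6625; 0.816/0.6625 gives p = .218 (printed .218).
- Self-efficacy 2: (2.774 − 0.377)/3.92 = 0.6115; 1.576/0.6115 gives p = .010 (printed .010).
- Non-barrier 1: (2.338 − 0.043)/3.92 = 0.5855; 1.190/0.5855 gives p = .042 (printed .042).
- Non-barrier 2: the printed interval (0.529 to 2.544) has midpoint 1.537 and is not centred on 1.711. The lower limit gives SE = (1.711 − 0.529)/1.96 = 0.603 and p = .0046, which agrees with the printed .005. The full width gives SE = 0.514 and p = .0009, which does not. I use 0.603. The upper limit of this interval should be checked separately.

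Shift = (jack-knife estimate − full estimate)/SE, at the two ends of each printed range:

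| Parameter | Full estimate | Jack-knife range | Shift in SE | Shift in % | Printed p range |
|---|---|---|---|---|---|
| Self-efficacy 1 | 0.816 | 0.477 to 1.086 | −0.51 to +0.41 | −41.5 to +33.1 | .098 to .408 |
| Self-efficacy 2 | 1.576 | 1.269 to 1.729 | −0.50 to +0.25 | −19.5 to +9.7 | .006 to .037 |
| Non-barrier 1 | 1.190 | 1.128 to 1.350 | −0.11 to +0.27 | −5.2 to +13.4 | .024 to .063 |
| Non-barrier 2 | 1.711 | 1.511 to 1.936 | −0.33 to +0.37 | −11.7 to +13.2 | .003 to .012 |

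With SE = 0.514 the last row becomes −0.39 to +0.44 SE, still under 0.5. Every range lies above zero and inside the corresponding full-model interval.

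**4. Why the p-value is a poor gauge for non-barrier 1.** With the SE held at 0.5855, p = .05 is reached at 1.96 × 0.5855 = 1.148. That is a fall of about 0.042 from 1.190, or 3.6% and 0.07 SE. A very small movement is enough to cross the line.

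**5. Control-clinic deletions.** The corresponding ranges need participant data. They cannot be derived from Table 2 or from any other figure in the document.

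**The case against.** The strongest defence is that context already limits the conclusion. The section is about heterogeneity of the treatment effect, and the app was used only in the 9 intervention clinics. Variation in how it was delivered or received can arise only there, so deleting those clinics is a sensible choice for that question. The method is stated openly more than once, including directly before Table 2, and the conclusion is hedged. The check is also supplementary: it touches no estimand, sample size or primary test.

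Most of this stands. The method is disclosed and coherent, and the practical weight of the point is modest. It does not remove the mismatch, because the stated purpose and the closing sentence both refer to recruitment site without restriction, and the quantity tested is a between-arm contrast.

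Two stronger readings are tempting, and the document supports neither.

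- A reader might infer that a control clinic drives the result, or that the effect is fragile. No control-clinic deletion is reported, so there is no evidence either way.
- A reader might take the .063 for non-barrier 1, or the 41.5% fall for self-efficacy 1, as proof of site sensitivity. The first goes with a fall in the estimate of at most 0.11 SE. The second is a shift of 0.51 SE in a parameter whose full-model interval already includes zero and which was non-significant in every model.

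Table 2 prints ranges rather than estimate and p-value pairs, and the document gives no clinic sizes. The cause of the spread in p-values therefore cannot be worked out further.

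**Conclusion.** The point holds as a mismatch of scope. The robustness claim is worded for recruitment site in general, while the evidence comes from deleting single intervention clinics, 9 of the 18 randomized. For those deletions the results are reassuring in direction and size. The only borderline result is non-barrier parameter 1. The influence of the control clinics is unknown.

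The mismatch itself rests on the text alone. The shifts in SE units assume normal-theory intervals, and for non-barrier parameter 2 they also depend on taking the SE from the lower limit. Nothing here implies that the estimated treatment effect is wrong.

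**What to change.** Extend the jack-knife to all 18 clinics by adding the 9 control-clinic deletions for each outcome, with imputation and variance estimation handled as in the existing 9 models. Report the estimate and p-value ranges separately for intervention-clinic and control-clinic deletions. Judge sensitivity mainly by the shift in the estimate rather than by whether p crosses .05.

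Until that is done, replace the closing sentence with one along these lines: *When single intervention clinics were deleted, all estimates stayed positive and within the full-model confidence intervals, and parameter 2 stayed below .05 for both outcomes; non-barrier parameter 1 was borderline (p .024 to .063 around .042). The influence of control clinics was not assessed.*

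The cost is 9 further fits for each of two outcomes, 18 in total, using existing code. The interim step costs one reworded statement. The primary analysis is unchanged.

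### Table 2: the upper 95% limit for non-barrier contraception, interaction parameter 2 (2.544), does not fit the rest of its row, which implies about 2.893

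*Combined protocol and SAP*

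**What the plan says.** The combined protocol and SAP, under Heterogeneity of Treatment Effects, presents Table 2 with two interaction parameters for each of two primary outcomes. The three main figures in each row have one source: "Table 2 reports the point estimate, 95% confidence interval, and p-value for each parameter obtained from the mixed effects regression analysis model". The remaining columns give the range of estimates and p-values when each intervention clinic is left out in turn.

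The same section gives these parameters their role: "For both outcomes, the time by treatment group interaction served as the direct test of the intervention effect". For non-barrier contraception (Aim 3b, Primary Outcome 3), parameter 2 is printed as estimate 1.711, 95% CI 0.529 to 2.544, p=.005, with leave-one-clinic-out estimates of 1.511 to 1.936 and p-values of .003 to .012.

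Under Analytical and statistical approaches, the model for this outcome is "mixed effects logistic regression to assess non-barrier contraception use". On variance, the section says: "Computation of p-values was based on robust variance estimation that adjusted for a potential lack of independence between observations due to clustering". It gives no rule for forming confidence intervals, and nothing in the document describes a profile-likelihood, bootstrap or other asymmetric interval.

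**The concern.** An interval of the form estimate ± multiplier × SE has the estimate at its centre. In this row the centre of the printed interval is (0.529 + 2.544)/2 = 1.5365, not 1.711. The other row for the same outcome and model is centred on its estimate, so the logistic model does not account for the exception.

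At stake is the stated precision of one of the two parameters that carry the test for a primary outcome. The printed interval looks tighter on the upper side than the row's own p-value allows. Anyone recovering a standard error from the interval, for instance for a meta-analysis, would get 0.514 and p=.0009 instead of about 0.603 and p=.005.

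**Working it through.** **Inputs.** All are from Table 2: estimate, 95% limits and p-value for each of the four rows, and the leave-one-clinic-out ranges for the disputed row. The reference distribution is normal, with multiplier 1.960.

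**Step 1: find the table's convention.** For each row, compute the lower half-width (estimate − lower), the upper half-width (upper − estimate), SE = width/(2 × 1.960), and two-sided p from z = estimate/SE.

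| Row | Lower half | Upper half | SE from width | p from width | p printed |
|---|---|---|---|---|---|
| Self-efficacy, 1 | 1.298 | 1.299 | 0.6625 | .2181 | .218 |
| Self-efficacy, 2 | 1.199 | 1.198 | 0.6115 | .0100 | .010 |
| Non-barrier, 1 | 1.147 | 1.148 | 0.5855 | .0421 | .042 |
| Non-barrier, 2 | 1.182 | 0.833 | 0.514 | .0009 | .005 |

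The first three rows reproduce as symmetric normal-reference intervals to the last printed digit. The fourth does not.

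**Step 2: find which cell is out of line.** Change one entry at a time in the fourth row.

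- Upper limit: SE = 1.182/1.960 = 0.603; z = 1.711/0.603 = 2.837; p = .0046, which prints as .005. This fits.
- Lower limit: SE = 0.833/1.960 = 0.425; z = 4.026; p = .00006, with an implied lower limit of 0.878. This does not fit.
- Estimate: moved to the midpoint 1.5365 with SE 0.514, p = .0028, which would print as .003. This does not fit.
- p-value: whatever its value, the interval stays off-centre. This does not fit.

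Only a change to the upper limit reconciles the row.

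**Step 3: the implied value.** By symmetry, upper = 2 × 1.711 − 0.529 = 2.893. Rounding of the inputs allows 2 × 1.7105 − 0.5295 = 2.8915 to 2.8945. A second route uses the p-value alone: p between .0045 and .0055 gives SE 0.602 to 0.616, so an upper limit of 2.891 to 2.919 and a lower limit of 0.531 to 0.503. That range contains the printed 0.529. Rounding cannot bridge the gap to 2.544.

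**Step 4: size.** The upper limit differs by 2.893 − 2.544 = 0.349. The width is 2.015 printed and 2.364 implied; (2.364 − 2.015)/2.364 = 14.8%. If the coefficient is on the logit scale, as the model description indicates, the limits exponentiate to a ratio of odds ratios of exp(2.544) = 12.7 and exp(2.893) = 18.0.

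**Step 5: a look at the leave-one-clinic-out columns.** No printed p is below .003, so the fit with estimate 1.936 has an SE of at least 1.936/z(.0025) = 0.640, where z(p) is the two-sided normal quantile. No estimate is below 1.511, so the fit with p=.012 has an SE of at least 1.511/z(.0115) = 0.598. Both exceed 0.514. These fits each drop a clinic, so this is supporting evidence and not an exact check.

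**The case against.** The strongest reply is that the document never says how its intervals were formed. It ties robust variance to p-values only, so symmetry is inferred from three rows. That is true, and the size of the discrepancy is conditional on it. The inference is strong, however: three rows fit to the last digit, one of them from the same model, and no asymmetric method is described anywhere.

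Multiple imputation was used for the regression models, and pooled results may use a t reference specific to each parameter. With the same lower limit, 100 degrees of freedom would give p=.0050 and 30 would give .0060, so the SE of 0.603 and p of .0046 do depend on the normal reference. But a t-based interval is still symmetric, so 2.544 is not rescued. The value 2.893 needs symmetry only.

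The leave-one-clinic-out evidence is limited. The table prints ranges and does not pair estimates with p-values, and an SE of 0.603 with estimate 1.936 gives p=.0013, below the smallest printed value. SEs can also shift when a clinic is dropped. For self-efficacy parameter 1, the fit with estimate 0.477 must have an SE of at most about 0.578, against 0.6625 in the full model, some 13% lower. What stands is the direction: both lower bounds lie above 0.514. The main argument does not need this support.

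Table 2 reports no odds ratios, so the exponentiated figures are a reading of the model description. A text-extraction fault cannot be formally excluded, although the row is intact and the two values differ in three digits.

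Finally, this is one cell and no conclusion turns on it. That bears on its weight. It is nonetheless a wrong error bar on a primary-outcome result, not a slip in background text.

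**Conclusion.** The point holds. As printed, the row is internally inconsistent, and the upper limit is the only single entry whose correction restores agreement. The implied limit is about 2.893, 0.349 above the printed value, which makes the printed interval about 15% too narrow. This rests on the interval being symmetric about the estimate, as in the other three rows, and on the estimate, lower limit and p-value being correct. The SE and p-value figures also assume a normal reference.

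The consequence is confined to stated precision. The lower limit stays above zero, p=.005 stands, and the conclusion that the effect is not sensitive to clinic is unchanged.

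**What to change.** Check the upper limit for non-barrier contraception, interaction parameter 2, against the model output. If the estimate, lower limit and p-value are confirmed, replace the interval with 0.529 to about 2.893, taking the exact figure from the output. If the interval came from a method that is not symmetric about the estimate, name that method and explain why it applies to this row only. One sentence stating how all the Table 2 intervals were computed would settle the matter for readers.

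The cost is one table cell checked against existing output, with no re-analysis. The stated precision of this parameter becomes somewhat less favourable.
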